3.0 INTRODUCTION

Study RAP-MD-01 is a Phase 3, multi-center, randomized, double-blind, placebo-controlled, parallel-group study in patients who are 18 to 65 years of age, meet DSM-5 (Diagnostic and Statistical Manual of Mental Disorders, Fifth Edition) criteria for Major Depressive Disorder (MDD), have a minimum score of 25 on the Montgomery-Åsberg Depression Rating Scale (MADRS), and have an ongoing inadequate response to antidepressant therapy (ADT).

[figure not shown]
The study will consist of up to a 14-day screening and washout period followed by a 1-week placebo lead-in period, a 2-week randomized treatment period, and then a 1 week of safety follow-up period. Both the placebo lead-in period and randomized treatment period will be conducted in a double-blind (DB) manner. Consequently, the combination of these two periods is referred to as the DB treatment period.

Signed informed consent from the patient or the patient's legally authorized representative will be obtained before any study-related procedures are begun. At the end of the screening period, patients meeting the eligibility criteria for this study will be enrolled into a 1-week, double-blind, placebo lead-in period intended to identify placebo responders. Placebo responders will be defined by meeting at least 1 of the following criteria at any time point during the 1-week double-blind placebo lead-in:

[figure not shown]
- Patients with $\geq 50\%$ decrease from Day 0 MADRS total score
- Patients achieving a MADRS total score of ≤ 14 points

Upon completion of the placebo lead-in period, patients will be randomized in 1:1 ratio to receive either rapastinel 450 mg or placebo, adjunctive to ongoing ADT. Randomization will be stratified by patient's responder status (as placebo non-responder vs. placebo responder) achieved during the end of the placebo lead-in period. The schedule of visits and procedures for study RAP-MD-01 is presented in [Table 3-1](#). The study design is shown graphically in [Figure 3-1](#).

This SAP provides a more technical and detailed elaboration of the statistical analyses of efficacy and safety data as outlined and/or specified in the final study Protocol Amendment 2 (version dated 12OCT2018), Amendment 3 (version dated 07DEC2018), the Restricted Access Addendum Amendment 2 (version dated 12OCT2018), and Amendment 3 (version dated 07DEC2018). Specifications of tables, figures, and data listings are contained in a separate document.

RES

[figure not shown]
4.0 OBJECTIVES

[figure not shown]
The objectives of this study are to evaluate the efficacy, safety, and tolerability of rapastinel adjunctive to ADT in patients with MDD.

Efficacy Objectives

The “baseline” referred in the following efficacy objectives is defined as the last measurement prior to the first dose of randomized IP.

- **Primary efficacy objective:** To evaluate the efficacy of rapastinel (450 mg IV) versus placebo in the treatment of MDD as an adjunct to ongoing ADT, as measured by the change from baseline to Day 21 in MADRS total score.
- **Key secondary efficacy objectives:**
 - To evaluate the efficacy of rapastinel (450 mg IV) versus placebo in the treatment of MDD as an adjunct to ongoing ADT, as measured by the change from baseline to Day 8 in MADRS total score (1 Day after the first randomized treatment).
 - To evaluate the efficacy of rapastinel (450 mg IV) versus placebo in the treatment of MDD as an adjunct to ongoing ADT, as measured by the change from baseline to Day 21 in MADRS total score for placebo non-responders.
 - To evaluate the efficacy of rapastinel (450 mg IV) versus placebo in the treatment of MDD as an adjunct to ongoing ADT, as measured by the change from baseline to Day 8 in MADRS total score (1 Day after the first randomized treatment) for placebo non-responders.

RESTRICTED

5.0 ANALYSIS POPULATIONS

The following populations will be considered in the statistical analysis of the study.

5.1 ENROLLED POPULATION

The Enrolled Population will consist of all patients who signed informed consent, received a patient identification number, entered into screening and received 1 dose of investigational product (IP) during the double-blind treatment period.

5.2 SAFETY POPULATION

The Safety Population will consist of all patients who were randomized and received at least 1 dose of IP during the randomized treatment period.

5.3 MODIFIED INTENT-TO-TREAT POPULATION

The modified Intent-to-Treat (mITT) Population will consist of all patients who were randomized, received at least 1 dose of IP during the randomized treatment period, and had at least 1 post-randomization assessment of the MADRS total score.

6.0 PATIENT DISPOSITION

The number of patients in the Enrolled, Safety and mITT populations will be summarized by treatment group and by study center.

Screen-failure patients (ie, patients screened but not included in the enrolled population) and their associated reasons for failure to enroll will be tabulated overall for all screened patients.

The number and percentage of patients in the mITT population who complete the randomized treatment period, of patients who prematurely discontinue during the same period and who entered the safety follow-up period will be presented for each treatment group and pooled across treatment groups for placebo lead-in period responders and non-responders both separately and combined. The reasons for premature discontinuation during the randomized treatment period as recorded on the disposition pages of the electronic case report forms (eCRFs) will be summarized by treatment group and placebo lead-in period responder status for the mITT Population.

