9.7.2 Patient Disposition

The number and percentage of patients in the Enrolled, Safety, and mITT populations will be summarized by treatment group and study center.

Screen-failure patients (ie, patients screened but not included in the Enrolled Population) and the associated reasons for failure will be tabulated overall for all screened patients.

The number and percentage of patients in the mITT Population who complete the double-blind treatment period and of patients who prematurely discontinue during the same period will be presented for each treatment group and pooled across treatment groups. The reasons for premature discontinuation during the double-blind treatment period as recorded on the disposition pages of the eCRFs will be summarized by treatment group for the mITT Population.

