9.0 EFFICACY ANALYSES

All efficacy analyses will be based on the mITT Population, unless stated otherwise. The baseline for each specific efficacy endpoint is defined as the last measurement prior to the first dose of randomized treatment. The Day 0 measure for each specific efficacy endpoint is defined as the last measurement prior to the first dose of double-blind IP in the placebo lead-in period. The analyses for the placebo lead-in period will be presented for all patients combined and separately for the placebo responders vs. non-responders using the Enrolled Population. All statistical hypothesis tests will be performed at the 2-sided 5% significance level for main effects. All confidence intervals (CIs) will be 2-sided 95% CIs, unless stated otherwise.

For efficacy analyses in which study center is a factor, a *small center* will be defined as a center with less than 2 placebo non-responder patients in at least 1 treatment group in the mITT Population. Small centers will be pooled to form pseudo-centers so that each treatment group includes at least 2 placebo non-responder patients within the center for the mITT population. Pooling will be done using the following algorithm:

Based on the number of placebo non-responder mITT patients, small centers will be ordered from the largest to the smallest, and centers of the same size will be ordered from the largest center number to the smallest center number. The pooling process starts with the largest small center from the top, which will be pooled with the smallest from the bottom until a non-small center is formed. The process will be repeated using the small centers left out after the first pass. If any centers are left out at the end of the process, they will be pooled with the smallest pseudo-center. If there is more than 1 smallest pseudo-center, the pseudo-center with the smallest center number will be selected. In case the pseudo-center formed by pooling all small centers is still a small center, it will be pooled with the smallest non-small center. If there is more than 1 smallest non-small center, the one with the smallest center number will be selected.

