While the study was ongoing, the primary efficacy variable was revised to be the change from baseline in MADRS score at the last visit, Day 21, and the primary efficacy study population was revised to include all randomized patients (placebo responders and placebo non-responders) based on the feedback by the FDA, EMA, and PDMA. Both of these changes were included in Amendment 2 of the protocol. At the same time of Amendment 2, a blinded data review was conducted for Studies RAP-MD-01, RAP-MD-02, and RAP-MD-03. The pooled SD for the three studies were 7.4, 8.0, and 8.7, respectively, all smaller than the originally assumed 10 points. Sample size was re-calculated using 8.7 as the common SD. The calculation used MMRM model with simulations; it also assumed correlation of 0.5 between the repeated measures and a common drop-out rate of 10% during the randomized treatment period and an additional 5% drop-out rate during the placebo lead-in period for all treatment groups. To have 90% power, the total sample size required is 360 patients. However, the study had already enrolled more than 440 patients with less than 5% of overall drop-out rate, surpassing the re-estimated sample size of 360 patients. The study enrollment was halted as soon as operationally feasible. The final sample size is approximately 460 patients (230 patients per treatment group).

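### Completion, discontinuation and reasons are tabulated on mITT only, so randomized patients who leave before any post-randomization MADRS are missing from those tables

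*SAP*

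**What the plan says.** SAP 6.0 has three parts. It first counts the Enrolled, Safety and mITT populations by arm and center. It then gives "The number and percentage of patients in the mITT population who complete the randomized treatment period", with premature discontinuation and entry into safety follow-up on the same set. Finally, the reasons for discontinuation "will be summarized by treatment group and placebo lead-in period responder status for the mITT Population". Protocol 9.7.2 has the same structure: "The number and percentage of patients in the mITT Population who complete the double-blind treatment period", with reasons that "will be summarized by treatment group for the mITT Population". The SAP therefore follows the protocol here.

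SAP 5.3 limits mITT to patients who were randomized, received a dose in the randomized period, and "had at least 1 post-randomization assessment of the MADRS total score". SAP 5.0 defines only the Enrolled, Safety and mITT populations. The change history in SAP 2.0 records that the Randomized and Intent-to-treat populations were removed.

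For efficacy, SAP 9.0 states: "All efficacy analyses will be based on the mITT Population, unless stated otherwise". The pattern-mixture sensitivity analysis in SAP 9.1 and Appendix II names no other set, so it also runs on mITT.

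**The concern.** A discontinuation table should show how many randomized patients left each arm, and why. Both conditions for entering mITT are met only after randomization, and a patient who leaves very early can fail either one. That patient has discontinued but is not in the table that counts discontinuations.

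At stake are the all-randomized completion and discontinuation rates by arm, and the reasons given by the earliest leavers. Protocol 9.3.3 lists withdrawal of consent, lack of efficacy and loss to follow-up among the possible reasons. No visible part of either document summarizes these for patients outside mITT. If such losses differed between arms, the disposition tables would not show it.

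**Working it through.** **1. Who is missing, and where they can still be seen**

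| Randomized patient | In the SAP 6.0 completion and reasons tables? | Visible elsewhere |
|---|---|---|
| Never given a randomized dose | No | Outside Safety and mITT; no table of reasons |
| Dosed, leaves for an AE, no later MADRS | No | AE tables by arm and AE listings (SAP 10.1); doses received (SAP 8.1); Safety minus mITT count (SAP 6.0) |
| Dosed, leaves for another reason, no later MADRS | No | Doses received and Safety minus mITT count only; no reason shown |
| Dosed, leaves, but has any later MADRS, including at early termination | Yes | Not needed |

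The gap is in rows one and three. For row two, only the entry in the reasons table is lost.

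**2. Direction of the error**

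Let N be the number randomized, D the number who discontinue, and k those of the D with no qualifying MADRS or no randomized dose. Then

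(D − k)/(N − k) − D/N = −k(N − D)/[N(N − k)], which is never positive.

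Within an arm the mITT rate can equal the all-randomized rate or fall below it. It cannot exceed it. This takes every excluded patient to be a non-completer.

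**3. Illustration of size**

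N = 460 is the final sample size (Protocol 9.7.9, SAP 13.0). D = 23 is 5% of 460, the ceiling implied by the statement that overall drop-out was below 5%. The share of D lost before a first MADRS is not given, so k is an assumption:

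- k = 0: 23/460 = 5.0%
- k = 6 (about a quarter): 17/454 = 3.7%
- k = 12 (about half): 11/448 = 2.5%
- k = 23 (all): 0/437 = 0%

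This shows how the table behaves. It does not estimate what happened.

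**4. The plan's sample size, as a check on the inputs**

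Inputs: SD 8.7, 90% power, two-sided 5%, and a difference of 3.25. The last is stated for the original design and assumed here to carry over. Per arm, 2 × (1.960 + 1.282)² × 8.7²/3.25² = 150.6, rounded up to 151. Allowing 15% loss, 151/0.85 gives 178 per arm, 356 in total. Compounding the SAP's 5% and 10% gives 354. Both agree closely with the stated 360, which came from MMRM simulation.

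With 460 patients and 5% loss (218.5 per arm), the standard error is 8.7 × √(2/218.5) = 0.83, and power is Φ(3.25/0.83 − 1.96), about 97%. The point raises no power problem.

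**5. Effect on the missing-data sensitivity analysis**

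Appendix II uses one common shift, with values from 0 to 8 (SAP 9.1). Equal numbers of excluded patients in each arm would largely cancel. At a shift of 8 the change in the treatment difference is about 8 × (imbalance in excluded patients)/230:

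- 1 patient: 8/230 = 0.03 points
- 3 patients: 24/230 = 0.10
- 6 patients: 48/230 = 0.21

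The unadjusted standard error is 8.7 × √(2/230) = 0.81. The calculation treats the full 8 points as present at Day 21. Appendix II instead carries the shift forward through regression on earlier values and re-applies it only with some probability, so these are round figures.

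**The case against.** The strongest reply is that little is hidden and few patients are likely to be affected. SAP 10.1 tabulates adverse events leading to discontinuation by arm and lists the patients. The protocol synopsis bases safety analyses on the Safety Population, which needs a dose but no MADRS. SAP 6.0 and 8.1 give population counts and doses received by arm. The first post-randomization MADRS is due one day after the first randomized dose (SAP 15.1). Protocol 9.1.2 requires everyone who receives IP to complete Visit 11, and Protocol 9.3.3 asks for an early-termination visit with the Visit 11 evaluations. One MADRS at any later visit keeps a patient in mITT. All of this stands. It narrows the point to the all-randomized rates and the non-AE reasons, but no visible table supplies those.

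Stronger readings are tempting, and the documents do not support them:

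- A reader might infer that an early loss caused by an adverse event of rapastinel disappears from the report. It is missing from the reasons table, but SAP 10.1 shows it by arm.
- A reader might take SAP 13.0, where "the primary efficacy study population was revised to include all randomized patients (placebo responders and placebo non-responders", as a promise of an intent-to-treat set. The General Notes in SAP 2.0 describe the same change as a move from placebo non-responders to mITT. The phrase is loose wording for pooling responders with non-responders.
- A reader might assume that 1% to 2% of 460 patients (5 to 9) are excluded and conclude that 22% to 39% of dropouts (5/23 to 9/23) go uncounted. The numerator has no source. The denominator is a ceiling and may include patients lost in the placebo lead-in, who were never randomized.
- A reader might infer that the robustness check is seriously compromised. Adding 8 points to a placebo mean for 2% of the rapastinel arm lowers the difference by 0.02 × (3.25 + 8) = 0.23, but that is not the SAP's method. Under the common shift, the same one-sided 2% gives 0.02 × 8 = 0.16, and balanced exclusion gives about zero.

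**Conclusion.** The point holds as a reporting gap. Completion, discontinuation and reasons are conditioned on a post-randomization MADRS, so the rates can only be understated, and the non-AE reasons of the earliest leavers have no visible table. The size cannot be computed from the documents and is probably small.

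The primary analysis is not in question: a patient with no post-randomization value contributes no outcome to an observed-case MMRM. The same restriction applies to the pattern-mixture analysis, but its likely effect is minor, at about 0.03 points per patient of arm imbalance against an unadjusted standard error near 0.81. The conclusion rests on the visible text; redacted parts of the SAP could hold further summaries.

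**What to change.** In SAP 6.0, present completion, premature discontinuation and reasons for all randomized patients by assigned arm, overall and by lead-in responder status as already planned. The mITT version may be kept beside it. Because Protocol 9.7.2 also specifies mITT, list the change in SAP 16.0, which currently says that the listed additions are the only changes. The reasons are already recorded on the disposition eCRF pages, so no new data collection appears necessary.

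Keep the mITT MMRM as primary. Optionally, add a supplementary pattern-mixture run on all randomized patients with a baseline MADRS, treating those with only a baseline value as the earliest dropout pattern. Appendix II can take them if its first measurement is the baseline; it should state whether that is so.

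The cost is a changed denominator, a few lines of SAP text, a little extra programming and a slightly higher reported drop-out rate.

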6.1 PROTOCOL DEVIATIONS

Protocol deviations will be defined in Protocol Deviation Requirement Specification, including the classification of significance vs. non-significance. The number and percentage of patients with significant protocol deviations will be summarized by treatment group for the Enrolled Population. A listing of all significant protocol deviations will be provided.

7.0

DEMOGRAPHICS AND OTHER BASELINE CHARACTERISTICS

Demographic parameters and other baseline characteristics (eg, age, race, ethnicity, sex, weight, height, body mass index) will be summarized for all patients combined using the Enrolled Population, mITT Population, placebo responders of mITT Population, and placebo non-responders of mITT Population. An analogous analysis will be performed for baseline efficacy assessments.

Medical and surgical history, psychiatric history, previous treatment with psychotropic medication, and nondrug psychiatric treatment will be summarized by treatment group for the Safety Population.

The *World Health Organization (WHO) Drug Dictionary Enhanced* will be used to classify prior and concomitant medications by therapeutic class. *Prior medication* is defined as any medication taken before the date of the first dose of DB IP during the placebo lead-in period. *Concomitant medication* is defined as any medication taken on or after the date of the first dose of DB IP which is during the placebo lead-in period. If a medication started prior to the first dose of DB IP and continued into the placebo lead-in period, then this medication will be included in the analysis of prior and concomitant medications separately.

The number and percentage of patients with prior and concomitant medication use will be summarized by treatment group and Anatomical Therapeutic Chemical code for the Safety Population.

Multiple medications used by a patient in the same category will be counted only once in the summary tables. Concomitant medications started after the last visit of the randomized treatment period will not be summarized but will be included in the data listings.

Prior ADT treatment in the current episode, as recorded on ATRQ, will be summarized by frequency counts and percentages for patients who took each ADT in adequate dose and duration, total number of ADT taken at adequate dose and duration (ie., 1, 2, 3 or >3), and percentage of improvement reported (ie., < 25%, 25% to 49%, 50% to 75%, or >75%).

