9.7.4 Extent of Exposure and Treatment Compliance

9.7.4.1 Extent of Exposure

Patients in the Safety Population will be categorized by the number of IP doses received. The number and percentage of patients in each category will be summarized by treatment group.

Prior medication is defined as any medication taken before the date of the first dose of randomized IP. *Concomitant medication* is defined as any medication taken on or after the date of the first dose of IP.

Both prior and concomitant medication use will be summarized by the number and proportion of patients in each treatment group receiving each medication within each therapeutic class for the Safety Population. Multiple medication use by a patient will only be counted once.

IV administration notes including site reaction at placement of IV, reaction to adhesive, infusion interruption, failure of administration device, increase in suicidality based on clinical evaluation, and perceptual disturbance based on mental status assessment are collected. For each item, the number and percentage of patients who had a 'yes' response will be summarized by treatment group and visit for the Safety Population. The number and percentage of patients taking each qualifying ADT will be summarized by treatment group for the mITT Population. Mean daily dose for each qualifying ADT will be summarized using descriptive statistics (number of patients, mean, standard deviation [SD], median, Q1, Q3, minimum, and maximum) by treatment group for the mITT Population.

9.7.4.2 **Measurement of Treatment Compliance**

Dosing compliance for the background ADT during a specified period is defined as the total daily dose administered to a patient during that period divided by the total daily dose prescribed during the same period multiplied by 100, as captured in the eCRF. Descriptive statistics for ADT compliance will be presented for each ADT and overall by treatment group for the mITT Population.

9.7.5 **Efficacy Analyses**

All efficacy analyses will be based on the mITT Population, unless stated otherwise. The baseline for each specific efficacy endpoint is defined as the last measurement prior to the first dose of randomized treatment. All statistical hypothesis tests will be performed at the 2-sided 5% significance level for main effects. All confidence intervals (CIs) will be 2-sided 95% CIs, unless stated otherwise.

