10.1 ADVERSE EVENTS

AEs will be coded using the *Medical Dictionary for Regulatory Activities* and reported separated for placebo lead-in, randomized treatment, and safety follow-up periods.

[figure not shown]
An AE (classified by preferred term) will be considered a treatment-emergent adverse event (TEAE) if it was not present before the first dose of DB IP (i.e. the first IP during the placebo lead-in period) or was present before the date of the first dose of DB IP and increased in severity after the first dose of DB IP. An AE that becomes serious after the date of the first dose of DB IP will also be considered as TEAE. If more than 1 AE was reported before the first dose of DB IP and coded to the same preferred term, the AE with the greatest severity will be used for comparison with the AEs occurring during each study period analyzed. An AE that occurred more than 30 days after the date of the last dose of DB IP (including the randomized IP) will not be considered as a TEAE.

[figure not shown]
The number and percentage of patients reporting TEAEs and TEAEs leading to study discontinuation in each treatment group will be tabulated by system organ class and preferred term and further categorized by severity and causal relationship to the IP. If more than 1 AE is coded to the same preferred term for the same patient, the patient will be counted only once for that preferred term using the greatest severity and strictest causality for the summarization by severity and causal relationship.

The incidence of common ($\geq 2\%$ of patients in any treatment group) TEAEs will be summarized by preferred term and treatment group and sorted by decreasing frequency for the test treatment.

A serious adverse event (SAE) that occurred between the date of the first dose of DB IP and 30 days after the date of the last dose of DB IP, inclusive, will be considered a treatment-emergent SAE (TESAE). The number and percentage of patients who have TESAEs will be summarized by preferred term and treatment group.

[figure not shown]
Listings will be presented for patients with SAEs, patients with AEs leading to discontinuation, and patients who die (if any). All patients with SAEs, including SAEs reported during the screening period and the safety follow-up period, and patients discontinuing because of AEs occurring before the start of randomized IP will be included in these listings.

[figure not shown]

[figure not shown]

[figure not shown]

RESTRICTED

RESTRICTED

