16.0 CHANGES TO ANALYSES SPECIFIED IN PROTOCOL

This SAP amendment includes additional analyses listed below. There are no other changes to the analyses specified in the final Protocol Amendment 2 (version dated 12 Oct 2018) and Amendment 3 (version dated 20NOV2018).

- Prior ADT use in current episode recorded on ATRQ (Section 7)
- Weight adjusted dose of rapastinel (section 8.4)

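### SAP 7.0 counts concomitant medication from the placebo lead-in dose and tabulates it by randomized arm with no stated split by period, which mixes pre-randomization with on-treatment use and dilutes any imbalance under treatment

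*SAP*

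**What the plan says.** The design in SAP 3.0 is a 1-week double-blind placebo lead-in, then 1:1 randomization, then a 2-week randomized treatment period.

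SAP 7.0 sets the medication rules:

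- The prior category "is defined as any medication taken before the date of the first dose of DB IP during the placebo lead-in period".
- The concomitant category covers "any medication taken on or after the date of the first dose of DB IP which is during the placebo lead-in period".
- Prior and concomitant use "will be summarized by treatment group and Anatomical Therapeutic Chemical code for the Safety Population". A patient counts once per category.
- The window closes at the end of randomized treatment: "Concomitant medications started after the last visit of the randomized treatment period will not be summarized but will be included in the data listings".

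The Safety Population is "all patients who were randomized and received at least 1 dose of IP during the randomized treatment period" (SAP 5.2).

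Elsewhere the SAP keeps the periods apart. Adverse events are "reported separated for placebo lead-in, randomized treatment, and safety follow-up periods" (SAP 10.1). Compliance with background antidepressant therapy is summarised by arm for the randomized treatment period (SAP 8.3). Lead-in efficacy data are shown for all patients together and by responder status, not by arm (SAP 9.0).

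Three other passages bear on the definitions. In Protocol 9.7.4.1, prior medication "is defined as any medication taken before the date of the first dose of randomized IP", while concomitant medication runs from the first dose of IP, without the word randomized. SAP 15.7 imputes incomplete medication start dates by reference to the first randomized dose. SAP 16.0 lists two additional analyses, neither about this definition, and adds: "There are no other changes to the analyses specified in the final Protocol Amendment 2".

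**The concern.** A by-arm table of concomitant medication is normally read as showing what else patients took while on their assigned treatment. Under SAP 7.0 it does not show that cleanly. A medicine taken and stopped during the lead-in sits in the rapastinel column although the patient had received no rapastinel. Because a patient counts once per category, it cannot be told apart from a medicine first needed after randomization.

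At stake is how well the report can show whether the arms stayed alike in other medication during the randomized weeks. The MADRS has items on sleep, inner tension and appetite (Protocol Appendix V), so use of medicines acting on these would matter when reading a Day 8 or Day 21 difference. That such medicines were permitted is an assumption, because the list in Protocol Appendix III is not shown in the available text.

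**Working it through.** The documents give no figure for this table, so there is none to reproduce. The check has three steps.

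**1. Who and what is counted.** The clock starts at the lead-in dose (Day 0), and the first randomized dose follows at about Day 7. So 7 of the 21 scheduled double-blind days, 7/21 = one third of the window, precede randomized treatment. Everyone in the Safety Population also has randomized-period time, so all randomized-period use is in the table too. The result is a mixture, not a loss of on-treatment data.

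**2. Effect on the arm difference.** For one medicine class, let r be the share of an arm using it in the randomized period and s the share using it only in the lead-in. The tabulated rate is r + s, and the tabulated difference is (r₁ − r₀) + (s₁ − s₀).

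Suppose a share q uses the class in the lead-in, equal in both arms (as randomization gives in expectation) and independent of later use. Then s = q(1 − r), the tabulated rate is 1 − (1 − q)(1 − r), and the difference is (1 − q)(r₁ − r₀).

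With assumed on-treatment rates of 10% (placebo) and 20% (rapastinel):

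| q | Placebo column | Rapastinel column | Difference | Lead-in-only share of rapastinel column |
|---|---|---|---|---|
| 0% | 10.0% | 20.0% | 10.0 points | 0% |
| 5% | 14.5% | 24.0% | 9.5 points | 4.0/24.0 = 17% |
| 10% | 19.0% | 28.0% | 9.0 points | 8.0/28.0 = 29% |
| 20% | 28.0% | 36.0% | 8.0 points | 16.0/36.0 = 44% |
| 30% | 37.0% | 44.0% | 7.0 points | 24.0/44.0 = 55% |

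As a gauge of visibility only, since no test is planned: at 230 per arm, a two-sided 5% comparison of 10% with 20% has power of about 0.85. The tabulated rates at q = 5%, 10% and 30% give 0.74, 0.63 and 0.33.

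Independence is not the only possible pattern. If lead-in-only users and later users do not overlap, say 5% of each arm in the lead-in and 8% v 4% later, the table shows 13% v 9%. The 4-point difference is unchanged, but the ratio falls from 8/4 = 2.0 to 13/9 = 1.44. If all lead-in use continues into the randomized period, s = 0 and nothing is distorted.

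**3. Date anchors.** SAP 7.0 classifies a medicine against the lead-in dose, but SAP 15.7.1 fills a missing start day with the day of the first randomized dose when month and year match. A medicine begun before the lead-in, in the same month as the first randomized dose and recorded without a day, is then dated to the first randomized dose. It drops out of prior medication and looks like a start under randomized treatment.

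**The case against.** The strongest reply is that this is a descriptive table which feeds no test, estimate or decision rule. Its anchor follows a convention: the first double-blind dose also anchors treatment-emergent adverse events, safety baselines and the rules for missing severity and causality. Other by-arm summaries partly cover the ground. Patients who start a new treatment after worsening must leave the study (Protocol 9.4.13), and discontinuations with reasons and significant deviations are tabulated by arm (SAP 6.0, 6.1). Table specifications are in a separate document (SAP 3.0) and might already include a display by period. All of this stands, and it keeps the severity low. It does not answer the attribution problem in SAP 7.0 itself, because adverse events share the same anchor and are nevertheless reported by period.

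A reader might infer two stronger points, and the documents support neither.

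- *That the table cannot show an imbalance under treatment.* It can. All randomized-period use is included, and in every pattern worked above the difference keeps its sign.
- *That the SAP moved the definition by a week without declaring it in SAP 16.0.* This is not established. The protocol's definition of concomitant medication refers to the first dose of IP, which SAP 7.0 matches. The public protocol describes no lead-in and places randomization and first dose at Visit 2 (9.4, 9.4.7.2), so its first randomized dose may be the same calendar dose that the SAP calls Day 0. The Restricted Access Addendum is not available, and the entry for Section 7.0 in the SAP's history of changes is redacted.

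**Conclusion.** The point holds as one of attribution and dilution. SAP 7.0, as written, counts medicines taken only in the pre-randomization week as concomitant in the rapastinel column, and no stated split separates them from use under randomized treatment. One third of the scheduled window is affected. With lead-in use equal across arms and independent of later use, the arm difference shrinks by the factor (1 − q). Under other patterns only the ratio changes, or nothing does.

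The usage rates and the permission of medicines that act on MADRS items are assumptions. The separate table specifications, the addendum and the redacted SAP text could not be checked. It would go too far to say that the table hides an explanation for a Day 8 or Day 21 result. Severity is low and the primary test is untouched.

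**What to change.** In SAP 7.0:

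1. Base the by-arm concomitant table on medicines taken from the first randomized dose to the last visit of the randomized treatment period.
2. Show medicines newly started in that interval separately.
3. Report lead-in medication for all patients combined, in the Enrolled Population, in line with how SAP 9.0 presents lead-in efficacy data.

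Reconcile the anchors in Protocol 9.7.4.1, SAP 7.0 and SAP 15.7, so that one stated dose governs both the classification of a medicine and the imputation of its dates. State how many of the new starts rest on an imputed start date, since the present rule can create them. If the separate table specifications already split by period, a cross-reference in SAP 7.0 would cover the display, and only the anchors would remain.

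The cost is SAP wording and one more descriptive table. Medication changes and additions are already recorded in the eCRF (Protocol 9.4.10), and SAP 15.7 already works with start and stop dates, so no new data are needed.
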